#### **10.1.5. Committees Structure**

##### **10.1.5.1. Data Monitoring Committee**

This study will not use an E-DMC.

#### **10.1.6. Dissemination of Clinical Study Data**

Pfizer fulfills its commitment to publicly disclose clinical study results through posting the results of studies on [www.clinicaltrials.gov](http://www.clinicaltrials.gov) (ClinicalTrials.gov), the EudraCT/CTIS, and/or [www.pfizer.com](http://www.pfizer.com), and other public registries and websites in accordance with applicable local laws/regulations. In addition, Pfizer reports study results outside of the requirements of local laws/regulations pursuant to its SOPs.

In all cases, study results are reported by Pfizer in an objective, accurate, balanced, and complete manner and are reported regardless of the outcome of the study or the country in which the study was conducted.

[www.clinicaltrials.gov](http://www.clinicaltrials.gov)

Pfizer posts clinical trial results on [www.clinicaltrials.gov](http://www.clinicaltrials.gov) for Pfizer-sponsored interventional studies (conducted in patients) that evaluate the safety and/or efficacy of a product, regardless of the geographical location in which the study is conducted. These results are submitted for posting in accordance with the format and timelines set forth by US law.

[EudraCT/CTIS](http://EudraCT/CTIS)

Pfizer posts clinical trial results on EudraCT/CTIS for Pfizer-sponsored interventional studies in accordance with the format and timelines set forth by EU requirements.

[www.pfizer.com](http://www.pfizer.com)

Pfizer posts CSR synopses and plain-language study results summaries on [www.pfizer.com](http://www.pfizer.com) for Pfizer-sponsored interventional studies at the same time the corresponding study results are posted to [www.clinicaltrials.gov](http://www.clinicaltrials.gov). CSR synopses will have personally identifiable information anonymized.

Documents within marketing applications

Pfizer complies with applicable local laws/regulations to publish clinical documents included in marketing applications. Clinical documents include summary documents and CSRs including the protocol and protocol amendments, sample CRFs, and SAPs. Clinical documents will have personally identifiable information anonymized.

Data sharing

Pfizer provides researchers secure access to participant-level data or full CSRs for the purposes of “bona-fide scientific research” that contributes to the scientific understanding of the disease, target, or compound class. Pfizer will make data from these trials available 24 months after study completion. Participant-level data will be anonymized in accordance with applicable privacy laws and regulations. CSRs will have personally identifiable information anonymized.

Data requests are considered from qualified researchers with the appropriate competencies to perform the proposed analyses. Research teams must include a biostatistician. Data will not be provided to applicants with significant conflicts of interest, including individuals requesting access for commercial/competitive or legal purposes.

#### **10.1.7. Data Quality Assurance**

All participant data relating to the study will be recorded on printed or electronic CRF unless transmitted to the sponsor or designee electronically (eg, laboratory data). The investigator is responsible for verifying that data entries are accurate and correct by physically or electronically signing the CRF.

Guidance on completion of CRFs will be provided in the CRF Completion Requirements document.

The investigator must ensure that the CRFs are securely stored at the study site in encrypted electronic and/or paper form and are password protected or secured in a locked room to prevent access by unauthorized third parties.

QTLs are predefined parameters that are monitored during the study. Important deviations from the QTLs and any remedial actions taken will be summarized in the CSR.

The investigator must permit study-related monitoring, audits, IRB/EC review, and regulatory agency inspections and provide direct access to source data documents. This verification may also occur after study completion. It is important that the investigator(s) and their relevant personnel are available during the monitoring visits and possible audits or inspections and that sufficient time is devoted to the process.

Monitoring details describing strategy, including definition of study-critical data items and processes (eg, risk-based initiatives in operations and quality such as risk management and mitigation strategies and analytical risk-based monitoring), methods, responsibilities, and requirements, including handling of noncompliance issues and monitoring techniques (central, virtual, or on-site monitoring), are provided in the data management plan and monitoring plan maintained and utilized by the sponsor or designee.

The sponsor or designee is responsible for the data management of this study, including quality checking of the data.

Records and documents, including signed ICDs, pertaining to the conduct of this study must be retained by the investigator for 15 years after study completion unless local regulations or institutional policies require a longer retention period. No records may be destroyed during the retention period without the written approval of the sponsor. No records may be transferred to another location or party without written notification to the sponsor. The investigator must ensure that the records continue to be stored securely for as long as they are maintained.

When participant data are to be deleted, the investigator will ensure that all copies of such data are promptly and irrevocably deleted from all systems.

The investigator(s) will notify the sponsor or its agents immediately of any regulatory inspection notification in relation to the study. Furthermore, the investigator will cooperate with the sponsor or its agents to prepare the investigator site for the inspection and will allow the sponsor or its agent, whenever feasible, to be present during the inspection. The investigator site and investigator will promptly resolve any discrepancies that are identified between the study data and the participant's medical records. The investigator will promptly provide copies of the inspection findings to the sponsor or its agent. Before response submission to the regulatory authorities, the investigator will provide the sponsor or its agents with an opportunity to review and comment on responses to any such findings.

#### **10.1.8. Source Documents**

Source documents provide evidence for the existence of the participant and substantiate the integrity of the data collected. Source documents are filed at the investigator site.

Data reported on the CRF or entered in the eCRF that are from source documents must be consistent with the source documents or the discrepancies must be explained. The investigator may need to request previous medical records or transfer records, depending on the study. Also, current medical records must be available.

Definition of what constitutes source data and its origin can be found in the Source Document Locator, which is maintained by the sponsor.

Description of the use of the computerized system is documented in the Data Management Plan, which is maintained by the sponsor.

The investigator must maintain accurate documentation (source data) that supports the information entered in the CRF.

The sponsor or designee will perform monitoring to confirm that data entered into the CRF by authorized site personnel are accurate, complete, and verifiable from source documents; that the safety and rights of participants are being protected; and that the study is being conducted in accordance with the currently approved protocol and any other study agreements, ICH GCP guidelines, and all applicable regulatory requirements.

#### **10.1.9. Study and Site Start and Closure**

The study start date is the date on which the clinical study will be open for recruitment of participants.

The first act of recruitment is the date of the first participant's first visit and will be the study start date.

The sponsor designee reserves the right to close the study site or terminate the study at any time for any reason at the sole discretion of the sponsor, including (but not limited to) regulatory authority decision, change in opinion of the IRB/EC, or change in benefit-risk assessment. Study sites will be closed upon study completion. A study site is considered closed when all required documents and study supplies have been collected and a study-site closure visit has been performed.

The investigator may initiate study-site closure at any time upon notification to the sponsor or designee/CRO if requested to do so by the responsible IRB/EC or if such termination is required to protect the health of study participants.

Reasons for the early closure of a study site by the sponsor may include but are not limited to:

- Failure of the investigator to comply with the protocol, the requirements of the IRB/EC or local health authorities, the sponsor's procedures, or the ICH GCP guidelines;
- Inadequate recruitment of participants by the investigator;
- Discontinuation of further study intervention development.

If the study is prematurely terminated or suspended, the sponsor shall promptly inform the investigators, the ECs/IRBs, the regulatory authorities, and any CRO(s) used in the study of the reason for termination or suspension, as specified by the applicable regulatory requirements. The investigator shall promptly inform the participant and should assure appropriate participant therapy and/or follow-up.

Study termination is also provided for in the clinical study agreement. If there is any conflict between the contract and this protocol, the contract will control as to termination rights.

#### **10.1.10. Publication Policy**

For multicenter trials, the primary publication will be a joint publication developed by the investigator and Pfizer reporting the primary endpoint(s) of the study covering all study sites. The investigator agrees to refer to the primary publication in any subsequent publications. Pfizer will not provide any financial compensation for the investigator's participation in the preparation of the primary congress abstract, poster, presentation, or primary manuscript for the study.

Investigators are free to publish individual center results that they deem to be clinically meaningful after publication of the overall results of the study or 12 months after primary completion date or study completion at all sites, whichever occurs first, subject to the other requirements described in this section.

The investigator will provide Pfizer an opportunity to review any proposed publication or any other type of disclosure of the study results (collectively, "publication") before it is submitted or otherwise disclosed and will submit all publications to Pfizer 30 days before submission. If any patent action is required to protect intellectual property rights, the investigator agrees to delay the disclosure for a period not to exceed an additional 60 days upon request from Pfizer. This allows Pfizer to protect proprietary information and to provide comments, and the investigator will, on request, remove any previously undisclosed confidential information before disclosure, except for any study-intervention or Pfizer-related information necessary for the appropriate scientific presentation or understanding of the study results. For joint publications, should there be disagreement regarding interpretation and/or presentation of specific analysis results, resolution of, and responsibility for, such disagreements will be the collective responsibility of all authors of the publication.

For all publications relating to the study, the investigator and Pfizer will comply with recognized ethical standards concerning publications and authorship, including those established by the International Committee of Medical Journal Editors. The investigator will disclose any relationship with Pfizer and any relevant potential conflicts of interest, including any financial or personal relationship with Pfizer, in any publications. All authors will have access to the relevant statistical tables, figures, and reports (in their original format) required to develop the publication.

#### **10.1.11. Sponsor's Medically Qualified Individual**

The contact information for the sponsor's MQI for the study is documented in the study contact list located in the supporting study documentation/study portal or other electronic system.

To facilitate access to their investigator and the sponsor's MQI for study-related medical questions or problems from non-study healthcare professionals, participants are provided with an ECC at the time of informed consent. The ECC contains, at a minimum, (a) protocol and study intervention identifiers, (b) participant's study identification number, (c) site emergency phone number active 24 hours/day, 7 days per week, and (d) Pfizer Call Center number.

The ECC is intended to augment, not replace, the established communication pathways between the participant and their investigator and site staff, and between the investigator and sponsor study team. The ECC is only to be used by healthcare professionals not involved in the research study, as a means of reaching the investigator or site staff related to the care of a participant. The Pfizer Call Center number is to be used when the investigator and site staff are unavailable. The Pfizer Call Center number is not for use by the participant directly; if a participant calls that number directly, they will be directed back to the investigator site.

## 10.2. Appendix 2: Clinical Laboratory Tests

The following safety laboratory tests will be performed at times defined in the [SoA](#) section of this protocol. Additional laboratory results may be reported on these samples as a result of the method of analysis or the type of analyzer used by the clinical laboratory, or as derived from calculated values. These additional tests would not require additional collection of blood. Unscheduled clinical laboratory measurements may be obtained at any time during the study to assess any perceived safety issues.

If possible, participants should be fasting for a minimum of 8 hours prior to all blood draws. However, if a participant is not fasting at a given visit, the blood draw should still be performed, and the non-fasting status should be documented.

**Table 2. Protocol-Required Safety Laboratory Assessments**

Hematology	Chemistry	Local Dipstick Urinalysis	Other
Hemoglobin Hematocrit RBC count Platelet count WBC count Total neutrophils (Abs) Eosinophils (Abs) Monocytes (Abs) Basophils (Abs) Lymphocytes (Abs)	BUN (urea) and creatinine eGFR using CKD-EPI equations Glucose (fasting) Calcium Sodium Potassium Chloride AST, ALT Total bilirubin Direct bilirubin Indirect bilirubin CK Alkaline phosphatase LDH (lactate dehydrogenase)	Protein (qual) Blood (qual) Nitrites Leukocyte esterase  Microscopy a	
 
Urine drug screeningb
 
Pregnancy test (β-hCG)c
 
 
At Screening Visit only:
 
 
FSHd
 
HbA1c
 

	For suspected DILIe AST/ALT T bili, direct and indirect bili Total bile acids, GGT Total protein, albumin Alkaline phosphatase CK PT, INR Acetaminophen/paracetamol or protein adduct levels Hepatitis serology		

- Only if UTI is suspected or urine blood, protein, nitrites, or leukocyte esterase is positive.
- The minimum requirement for drug screening includes cocaine, THC, opiates/opioids, PCP, barbiturates, benzodiazepines, and amphetamines (others are site and study specific).
- Serum or urine β-hCG for female participants of childbearing potential as indicated in the [SoA](#).
- For confirmation of postmenopausal status only.
- Additional tests may be needed for Hy's Law. See [Appendix 5](#) for detailed information. Participants may have to return to the study site to provide additional blood samples for these laboratory tests.

The investigator must review the laboratory report, document this review, and record any clinically relevant changes occurring during the study in the AE section of the CRF.

### 10.3. Appendix 3: Adverse Events: Definitions and Procedures for Recording, Evaluating, Follow-Up, and Reporting

#### 10.3.1. Definition of AE

AE Definition

 
• An AE is any untoward medical occurrence in a patient or clinical study participant, temporally associated with the use of study intervention, whether or not considered related to the study intervention.
 
• Note: An AE can therefore be any unfavorable and unintended sign (including an abnormal laboratory finding), symptom, or disease (new or exacerbated) temporally associated with the use of study intervention.
 

Events Meeting the AE Definition

 
• Any abnormal laboratory test results (hematology, clinical chemistry, or urinalysis) or other safety assessments (eg, ECG, radiological scans, vital sign measurements), including those that worsen from baseline, considered clinically significant in the medical and scientific judgment of the investigator. Any abnormal laboratory test results that meet any of the conditions below must be recorded as an AE:           
 
• Is associated with accompanying symptoms.
 
• Requires additional diagnostic testing or medical/surgical intervention.
 
• Leads to a change in study dosing (outside of any protocol-specified dose adjustments) or discontinuation from the study, significant additional concomitant drug treatment, or other therapy.
 
 
 
• Exacerbation of a chronic or intermittent preexisting condition, including an increase in either frequency and/or intensity of the condition.
 
• New condition detected or diagnosed after study intervention administration, even though it may have been present before the start of the study.
 
• Signs, symptoms, or the clinical sequelae of a suspected drug-drug interaction.
 
• Signs, symptoms, or the clinical sequelae of a suspected overdose of either study intervention or a concomitant medication. Overdose per se will not be reported as an AE or SAE unless it is an intentional overdose taken with possible suicidal/self-harming intent. Such overdoses should be reported regardless of sequelae.
 

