## 4. STUDY DESIGN

### 4.1. Overall Design

This is a Phase 3, randomized, double-blind, placebo-controlled, multicenter, single-attack, outpatient evaluation of the efficacy and safety of zavegepant versus placebo for the acute treatment of migraine in Asian adults. The study intervention is formulated as zavegepant 10 mg IN or matching placebo. The study intervention will be administered using an unidose nasal spray device containing a single dose of zavegepant or matching placebo. The

PFIZER CONFIDENTIAL

CT02-GSOP Clinical Protocol Template Phase 1 2 3 4 (01 April 2022)

Page 35

090177e19cb4b323\Approved\Approved On: 23-Feb-2023 06:46 (GMT)

participants will be instructed to take their study intervention, as an outpatient, if they have a migraine headache which reaches moderate or severe pain intensity.

The total duration of study participation will be up to approximately 16 weeks. This includes a 3-28 day Screening Phase, a Treatment Phase that can last up to 45 days or until the participant has a migraine headache that reaches moderate or severe pain intensity, followed by an EOT Visit 7 (+2) days after the administration of study intervention and a Follow-Up Visit 28-35 days after the administration of study intervention for safety monitoring.

Approximately 1750 participants will be screened to randomize approximately 1400 participants in a 1:1 ratio between the 2 treatment groups (zavegepant or placebo). Before any study procedures are performed, participants must sign informed consent. After informed consent is signed, participants will be enrolled in the IRT system. The participant's migraine history and medical history will be collected at the Screening Visit. Participants will also undergo all screening procedures as indicated in the SoA. Screening Visit must be completed in person.

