#### **8.4.1. Time Period and Frequency for Collecting AE and SAE Information**

The time period for actively eliciting and collecting AEs and SAEs (“active collection period”) for each participant begins from the time the participant provides informed consent, which is obtained before undergoing any study-related procedure and/or receiving study intervention, through and including a minimum of 28 calendar days after the last administration of the study intervention.

Follow-up by the investigator continues throughout the active collection period and until the AE or SAE or its sequelae resolve or stabilize at a level acceptable to the investigator.

When a clinically important AE remains ongoing at the end of the active collection period, follow-up by the investigator continues until the AE or SAE or its sequelae resolve or stabilize at a level acceptable to the investigator and Pfizer concurs with that assessment.

For participants who are screen failures, the active collection period ends when screen failure status is determined.

If the participant withdraws from the study and also withdraws consent for the collection of future information, the active collection period ends when consent is withdrawn.

If a participant permanently discontinues or temporarily discontinues study because of an AE or SAE, the AE or SAE must be recorded on the CRF and the SAE reported using the CT SAE Report Form.

Investigators are not obligated to actively seek information on AEs or SAEs after the participant has concluded study participation. However, if the investigator learns of any SAE, including a death, at any time after a participant has completed the study, and they consider the event to be reasonably related to the study intervention, the investigator must promptly report the SAE to Pfizer using the CT SAE Report Form.

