#### Follow-Up of AEs and SAEs

- The investigator is obligated to perform or arrange for the conduct of supplemental measurements and/or evaluations, as medically indicated or as requested by the sponsor, to elucidate the nature and/or causality of the AE or SAE as fully as possible. This may include additional laboratory tests or investigations, histopathological examinations, or consultation with other healthcare providers.
- If a participant dies during participation in the study or during a recognized follow-up period, the investigator will provide Pfizer Safety with a copy of any postmortem findings, including histopathology.
- New or updated information will be recorded in the originally submitted documents.
- The investigator will submit any updated SAE data to the sponsor within 24 hours of receipt of the information.

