Efficacy	
 
To further compare zavegepant with placebo for early return to normal function.
 
	
 
Percentage of participants with a functional disability level of normal at 15 minutes postdose, evaluated for participants with functional disability at the time of dosing.
 
	
 
The estimand is the treatment effect of zavegepant relative to placebo in terms of the difference in percentage of participants with a functional disability level of normal at 15 minutes postdose among all randomized participants with migraine headache of moderate or severe intensity who took study intervention and had functional disability at the time of dosing. Intercurrent event of taking rescue medication at or before 15 minutes postdose will be regarded as a failure.
 

Safety	
 
To evaluate the safety and tolerability of zavegepant in
 
	
 
Number and percentage of participants with AEs of moderate or severe intensity, SAEs, local irritation AEs, and
 
	
 
Not applicable.
 

Type	Objective	Endpoint	Estimand
	the acute treatment of migraine.	grade 3 or 4 laboratory test abnormalities.	
	Tertiary/Exploratory:	Tertiary/Exploratory:	Tertiary/Exploratory:
Efficacy	
 
To evaluate the time course of zavegepant efficacy vs placebo.
 
	
 
Percentage of responders at each of the assessed time points (15, 30, 45, 60, 90 minutes; 2, 3, 4, 6, 8, 24, and 48 hours) for each of the primary and secondary endpoints described above that assess a specific time point.
 
	
 
As described above for each primary and secondary endpoint, using the applicable time point.
 

Efficacy	
 
To estimate zavegepant relative to placebo for the PGIC ratings.
 
	
 
Percentage of participants with the overall status improvement at 30 minutes, 60 minutes, 2 hours and 24 hours postdose based on the total score of PGIC.
 
	
 
Not applicable.
 

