#### 6.6.1.2.1. Pre-treatment AEs

Pre-treatment AEs will not be summarized, and will be included in the AE listing.

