#### 6.6.1.2.2. On-Treatment Treatment Emergent AEs (TEAE)

An AE is considered a treatment-emergent AE if the event started after the study intervention start date/time. All-cause and treatment-related TEAEs will be summarized by SOC and PT for the safety analysis set by treatment group for the following endpoints:

- TEAEs
- TEAEs by severity (total, mild, moderate, severe, not reported)
- SAEs

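### The SAP defines a treatment-emergent AE by onset after dosing only, so an AE opened between consent and dosing that worsens after the spray can drop out of the TEAE tables

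*Protocol*

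**What the plan says.** **What counts as an AE.** Protocol 10.3.1 covers any sign, "symptom, or disease (new or exacerbated) temporally associated with the use of study intervention". Among the events that qualify it lists "Exacerbation of a chronic or intermittent preexisting condition, including an increase in either frequency and/or intensity of the condition".

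**When AEs are collected.** Under Protocol 8.4.1 active collection "begins from the time the participant provides informed consent". Protocol 4.1 says of total participation: "This includes a 3-28 day Screening Phase, a Treatment Phase that can last up to 45 days". An AE can therefore already be open when the dose is taken.

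**How an AE is recorded.** Protocol 10.3.3 has the investigator assign each AE to one of three intensity categories. Its follow-up section adds: "New or updated information will be recorded in the originally submitted documents".

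**What is tabulated.** SAP 6.6.1.2.2 states: "An AE is considered a treatment-emergent AE if the event started after the study intervention start date/time". SAP 6.6.1.2.1 states: "Pre-treatment AEs will not be summarized, and will be included in the AE listing". The overview (SAP 6.6.1.1), the SOC/PT, severity and SAE summaries (6.6.1.2.2 and 6.6.1.2.3) and the study-discontinuation summary (6.6.1.4) are all specified as TEAE summaries. The secondary safety endpoint in SAP 2.2 is the "Number and percentage of participants with AEs of moderate or severe intensity, SAEs, local irritation AEs, and" grade 3 or 4 laboratory abnormalities.

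**The concern.** The TEAE rule has one test, the start time. It has no second limb for an event that was already present and got worse, or became serious, after dosing. The protocol's own concept of an AE includes aggravation, and the main risk it names for this product (Protocol 2.3.1) is local: throat irritation, nasal congestion, nasal discomfort and dysgeusia. Aggravation by the spray of a mild nasal or throat complaint that began during the wait for an attack is a plausible form of that harm.

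If such an event keeps its predose start date, it is classed as pre-treatment and goes to the listing. A listing gives no count or percentage by arm, and a count and percentage by arm is what the secondary safety endpoint asks for. Any worsening caused by the drug would be lost more often from the zavegepant arm than from placebo.

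**Working it through.** The plan states no figure on this point, so the check is a comparison of texts.

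**Step 1. Can an AE be open at dosing?** Collection starts at consent. Screening lasts up to 28 days and the wait for a qualifying attack up to 45 days: 28 + 45 = 73 days. So yes.

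**Step 2. Follow each kind of worsening through the SAP rule.**

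- *(a) A medical-history condition that first worsens after dosing.* Under Protocol 10.3.1 the exacerbation is itself the AE. Its onset is the worsening, which is postdose. It meets SAP 6.6.1.2.2 and is counted.
- *(b) An AE opened between consent and dosing, with the worsening entered as a new AE record.* The new record has a postdose start and is counted.
- *(c) The same AE, with the worsening entered as an update to the existing record.* The start stays predose, so SAP 6.6.1.2.2 is not met and SAP 6.6.1.2.1 sends the event to the listing.
- *(d) As (c), but the AE becomes serious after dosing.* The SAE summaries sit under the TEAE headings, so the outcome is the same.

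The loss arises in (c) and (d) only. Neither document says whether a site should follow (b) or (c).

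**Step 3. Which tables are affected?** The overview, SOC/PT, severity, SAE and discontinuation tables are, because they are TEAE tables. For the other-significant-AE tables in SAP 6.6.1.3, which include local irritation, the answer is unclear. They are described by analysis period and do not use the term TEAE. SAP 5.2.4 gives the date limits of each period but not which AE date must fall inside them. Two narrower rules do use the AE start date: the dizziness concurrency rule in 6.6.1.3 and the liver-test concurrency rule in 6.6.2.2. If that convention were general, (c) and (d) would be missing here too.

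**Step 4. Size, as an illustration only.** All of these inputs are assumed, because the documents give no AE rates or durations: AE onset in 10% to 20% of participants per 28 days, mean duration D of 7 to 14 days, 30 days from consent to dose, and postdose worsening in 10% to 20% of open AEs.

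Share with an AE open at dosing = (rate/28) × D × (1 − exp(−30/D)).

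- Low: (0.10/28) × 7 × (1 − exp(−30/7)) = 0.025 × 0.986 = 0.0247. Of 630 per arm that is 15.5; times 10% it is 1.6 participants, or 0.25%.
- High: (0.20/28) × 14 × (1 − exp(−30/14)) = 0.100 × 0.883 = 0.0883. Of 630 per arm that is 55.6; times 20% it is 11.1 participants, or 1.8%.

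This is a gross count of AEs of any kind. It treats open events as participants, does not remove those already counted through another TEAE, and says nothing about the difference between arms.

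**The case against.** The strongest reply is that the protocol and SAP do not conflict. Protocol 10.3.1 makes the exacerbation an AE in its own right, and it excludes fluctuations of existing conditions only when they do not worsen. On that reading the event starts when the worsening starts, and a postdose worsening is a TEAE. This stands for medical-history conditions, case (a). A reader might infer from the two definitions that the SAP contradicts the protocol, and the documents do not support that.

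Second, the remaining loss depends on a recording convention. The sentence on updated information comes among bullets on further evaluations, postmortem findings and SAE updates, so it may concern report forms rather than AE onset dates. Protocol 10.1.7 refers to a CRF Completion Requirements document that is not among the documents reviewed and may say how to record worsening. This also stands. It makes the loss conditional but does not remove it, since the only text on updates points towards keeping the existing record.

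Third, a reader might infer that the event vanishes from every AE table. That goes too far. The tables in SAP 6.6.1.3 are not expressly limited to TEAEs. SAP 6.6.1.1 also speaks of an overview for each analysis period, although its next sentence narrows this to TEAEs on treatment and in follow-up. The event remains in the listing as well.

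Fourth, nausea would be a poor example. Expected symptoms of the migraine are not AEs under Protocol 10.3.1, and nausea is captured in the eDiary. Nasal and throat symptoms are better examples. Even there, significant nasal conditions are excluded at screening (Protocol 5.2) and the nose is inspected again at Baseline (8.3.2), so few nasal AEs should be open at randomization. Those checks do not reach complaints that begin during the following 45 days.

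**Conclusion.** The point holds in a limited form. As written, the TEAE rule omits an AE that opened between consent and dosing, is kept on one record with its predose start date, and intensifies or becomes serious after dosing. Such an event is absent from the TEAE overview and from the SOC/PT, severity, SAE and discontinuation tables. Whether the tables in SAP 6.6.1.3 also lose it cannot be settled from the text.

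The size cannot be derived from the documents. Under the assumed inputs it is about 2 to 11 participants per arm, before removing anyone already counted through another TEAE. It is probably small.

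A reader might go further and conclude that the safety difference between arms is understated. That would follow only if the spray itself causes worsening of open AEs. Spontaneous worsening should be similar in the two arms, and no arm difference can be calculated. The safety tables are descriptive and no efficacy conclusion depends on them. A worsening limb is nevertheless a better rule than onset alone, because the count would no longer depend on how a site recorded the event.

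**What to change.** In SAP 6.6.1.2.2, add that a TEAE is also an AE that started before dosing and increased in intensity or became serious after it. Count it at its postdose intensity, in the analysis period in which it worsened. Apply the same rule to the other-significant-AE tables in SAP 6.6.1.3, so that their treatment of such events is explicit.

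Check whether the CRF Completion Requirements already call for a new record, with its own start date, when an open AE worsens. If they do, say so in the SAP. Where the date of worsening was not captured, tabulate by arm the AEs open at dosing by worst intensity. That gives a comparison between groups without new data.

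The cost is one sentence in the SAP and one derived flag, or one extra table. The downside is slightly higher reported TEAE counts.
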